|  | 
randomized, double-blinded, placebo-controlled, phase II clinical trial (NCT01836094) to evaluate the effects of oral USP MB (280 mg) on memory and cognition by using cerebral blood flow (CBF), evoked functional MRI (fMRI) and resting-state functional connectivity fMRI (fcMRI) on young (30 yo) healthy volunteers. Our findings suggest the MB has favorable cognitive and memory effects. The subjects, 28 subjects to date, did not experience any negative adverse event.
 
There are also a few MB clinical trials in mild to moderate AD and dementia (NCT01689246, NCT01689233, NCT01626378). An abstract of a phase II clinical trial reported that daily oral doses of 300 mg non-reduced form of MB (methylthioninium chloride), under trade name “Rember” (TauRx Therapeutics, Inc.), slowed the progression of AD compared to placebo. Ongoing phase III clinical trials use a proprietary reduced form of methylene blue (leukomethylene blue, LMTX™, TauRx) in mild and moderate AD and variant frontotemporal dementia. Our clinical trial differs from these clinical trials in several aspects: (1) TauRx phase II and phase III trials enrolled subjects with mild to severe Alzheimer’s disease and frontotemporal dementia (no MCI). Our study will be the first phase II clinical trial using MB in MCI, where early intervention is likely more effective. (2) TauRx phase II clinical trial used a large number of subjects with mild to moderate Alzheimer’s dementia and a larger dose up to 300 mg daily for one year with Rember™ (non-reduced form of MB). Our phase II trial will offer a markedly lower sample size, lower dose, and shorter duration, enabled by objective and powerful fMRI readouts. (3) The TauRx phase III clinical trial uses LMTX™, a new reduced form of MB that is less well studied. Our phase II trial will use the non-proprietary non-reduced form of MB (methylthioninium chloride), which has been used in most preclinical studies and clinical trials. (4) Subjects will be recruited from among well-characterized participants and a large cohort in the Texas Alzheimer’s Research and Care Consortium (TARCC). These subjects all have longitudinal psychometrics, and serum protein biomarkers on file, and frozen serum samples and DNA stored for future analyses. (4) The TauRx trials target to inhibit tau aggregation in neurofibrillary tangles of AD and demented patients, whereas we target to support healthy cognitive function by increasing mitochondrial oxidative energy metabolism and reducing oxidative stress in aging individuals before onset of AD neuropathology and dementia.
 
Our proposed phase II trial is very similar to our current phase II trial (NCT01836094) except it now includes middle aged, MCI and Alzheimer’s disease subjects and daily MB dose for 2 to 12 weeks (as opposed to healthy subjects and single dose) as well as additional neuropsychological tests.
 |

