| 
Item 4
Purpose and rationale
Insert purpose, objectives and research questions/hypotheses here. If you cut and paste from another document, make sure the excerpted material answers the question
 | 
The purpose of the current IND proposal is to test the hypothesis whether daily oral MB for 2 to 12 weeks will improve memory, attention, cognition and functional connectivity in healthy middle aged, and healthy elderly as well as MCI and AD subjects by using objective MRI readouts and standard neuropsychological tests. subjects by using objective MRI readouts and standard neuropsychological tests. MRI readouts include evoked functional MRI (fMRI), cerebral blood flow (CBF), and resting-state functional connectivity fMRI (fcMRI). We will utilize a double-blinded, placebo-controlled phase II clinical trial.
 
MRI and neuropsychological tests will be administered over about 1.5 hours before oral MB, and again about 2 weeks after oral MB. The subject will have the option to continue for another 10 weeks after the completion of the first two weeks. The primary outcome measures will include fMRI readouts to assess episodic memory, working memory and sustained attention, respectively, before and two weeks after MB. Secondary outcome measures will include standard neuropsychological tests.
  |

|   |  |  |
|---|--|--|
| 
Item 5
Study Population(s) Being Recruited
 
In your recruitment plan, how many different populations of prospective subjects do you plan to target?
Provide number: 4
 | 
Identify the criteria for inclusion:
 | 
Identify the criteria for exclusion:
 |
|---|--|--|

|   |  |  |
|---|--|--|
| 
e.g., a population can be individuals with type 2 diabetes controlled with diet and/or a population of healthy controls. Or a population can be individuals attending an education program, etc.
 
List each different population on a separate row and provide a short descriptive label:
(e.g., normal-healthy, diabetics, parents, children, etc.)
 
To add rows use copy & paste
 |  |  |

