|  | 
Step-by-Step Methods: 
 
Adult volunteers will be studied using a randomized, double-blinded, placebo-controlled design. Placebo arms will be included for healthy middle aged, healthy elderly, MCI and AD groups as controls. USP Methylene blue (MB) and placebo pills will be compounded into blue immediate release capsules. The subject will take 3 pills of MB or placebo (94mg per pill) three times a day with each meal. Placebo will be FD&C Blue # 2 which is a powder similar to the powder form of methylene blue. Each arm will also receive a pill of phenazopyridine hydrochloride (97.5 mg, marketed as Azo Standard) with each daily dosage. Phenazopyridine is a safe OTC product used for urinary discomfort that turns urine brownish. This drug will be given to both MB and placebo groups so that both show similar urine discoloration. This choice of administration is justified not only to maintain the blind procedure but because it would prevent any mild discomfort experienced by MB urinary excretion during chronic treatment. The subject, person administering the drug, and data analysts will not know whether the intervention is placebo or MB. The design will only be unblinded at the last steps when necessary. All subjects will be told that the pill they take may or may not cause urine/feces discoloration depending on individual's metabolism.
 
Step by Step:
The healthy elderly, MCI and AD subjects will be recruited from the Texas Alzheimer's Research and Care Consortium (TARCC). A neuropsychological battery of tests (eg. logical memory I, logical memory II, verbal fluency/COWA, Instrumental Activities of Daily Living (IADL), Global Depressive Scale (GDS), etc.) will be administered for all subjects before MRI study (2 month window).
 
Baseline MRI scan will be performed during visit 1.
 
Subject will be given labeled pill organizers with pills to take on days 1 through 14. Subject will be contacted via telephone on days 3, 7 and 11 (<math>\pm 2</math> days) to document any adverse event or problem. After 2 weeks <math>\pm 3</math> days of MB (282 mg, oral x 14 days) or placebo, another neuropsychological tests and MRI scan will be obtained. On visit 2, the subject will be given the option to continue for another 10 weeks. During visit 3, after 10 weeks <math>\pm 3</math> days, the subject will complete the subset of neuropsychological tests completed in visit 1, and some of the MRI scans completed in visit 1.
 
For MRI, task-evoked BOLD fMRI, cerebral blood flow (CBF), resting-state fMRI, and CBF will be performed. For the task-evoked BOLD fMRI, subjects will perform the following scans while in the
 |

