#### Intervention Groups:

| Arms                                 | Assigned Interventions  |
|--------------------------------------|---|
| Experimental:
Healthy Middle Aged | Drug: Methylene Blue (USP grade, 282 mg oral, up to 12 weeks)
Phenazopyridine hydrochloride (97.5 mg oral, up to 12 weeks)             |
| Placebo: Healthy Middle Aged         | Drug: FD&C Blue # 2 (USP grade, 282 mg oral, up to 12 weeks)
Phenazopyridine hydrochloride (97.5 mg oral, up to 2 weeks)               |
| Experimental:
Healthy Elderly MB  | Drug: Methylene Blue (USP grade, 282 mg oral, once daily, up to 12 weeks)
Phenazopyridine hydrochloride (97.5 mg oral, up to 12 weeks) |
| Placebo: Healthy Elderly MB          | Drug: FD&C Blue # 2 (USP grade, 282 mg oral, up to 12 weeks)
Phenazopyridine hydrochloride (97.5 mg oral, up to 12 weeks)              |
| Experimental:
MCI MB              | Drug: Methylene Blue (USP grade, 282 mg oral, once daily, up to 12 weeks)
Phenazopyridine hydrochloride (97.5 mg oral, up to 12 weeks) |
| Placebo:
MCI MB                   | Drug: FD&C Blue # 2 (USP grade, 282 mg oral, up to 12 weeks)
Phenazopyridine hydrochloride (97.5 mg oral, up to 12 weeks)              |
| Experimental:
AD MB               | Drug: Methylene Blue (USP grade, 282 mg oral, up to 12 weeks)
Phenazopyridine hydrochloride (97.5 mg oral, up to 12 weeks)             |

Placebo:  
AD MB

Drug: FD&C Blue # 2 (USP grade, 282 mg oral, up to 12 weeks)  
Phenazopyridine hydrochloride (97.5 mg oral, up to 12 weeks)

**The daily 282mg of MB or place will be divided into three doses of 94mg each to minimize the risk for urinary irritation. A second pill of Azo will be taken during one of these doses.**

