**OUTCOMES:**

**Primary Outcome Measures:**

Working memory task fMRI measures

[Time Frame: baseline, 2 weeks ± 3 days, 12 weeks ± 3 days]

Delayed Match to Sample Task behavioral (ie. correct number of responses) and fMRI measures will be acquired simultaneously

Episodic memory task fMRI measures

[Time Frame: baseline, 2 weeks ± 3 days, 12 weeks ± 3 days]

Face-Name Task behavioral (ie. correct recalls) and fMRI measures will be acquired simultaneously

Sustained attention task fMRI measures

[Time Frame: baseline, 2 weeks ± 3 days, 12 weeks ± 3 days]

Psychomotor vigilance task behavioral (ie. reaction time) and fMRI measures will be acquired simultaneously

Neuropsychological Battery

[Time Frame: baseline, 2 weeks ± 3 days, 12 weeks ± 3 days]

TARCC designed psychometric tests

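### Visits 2 and 3 are fixed by calendar day only: the time from the last capsule to the scans and tests is neither standardised nor recorded, which limits precision, comparability and attribution

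*Combined protocol and SAP*

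**What the plan says.** **Timing of assessments.** Item 4 states that "MRI and neuropsychological tests will be administered over about 1.5 hours before oral MB, and again about 2 weeks after oral MB". Item 6 (Step by Step) places visit 2 at two weeks, plus or minus three days, when after a course "of MB (282 mg, oral x 14 days) or placebo, another neuropsychological tests and MRI scan will be obtained". Visit 3 follows ten weeks later with the same tolerance, and there "the subject will complete the subset of neuropsychological tests completed in visit 1, and some of the MRI scans completed in visit 1". Each primary outcome carries the frame "Time Frame: baseline, 2 weeks ± 3 days, 12 weeks ± 3 days". All of these are day windows. No section gives a clock time, an interval from the last capsule, an instruction on whether the visit-day capsule comes before the scan, or a record of when the last capsule was taken. The Data Analysis Plan has pre/post and treatment as factors and no term for time since dose.

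**Dosing.** Items 2 and 6 describe immediate-release capsules. Under Intervention Groups, the daily 282 mg "will be divided into three doses of 94mg each to minimize the risk for urinary irritation". The frequency is not stated consistently. Step by Step says "The subject will take 3 pills of MB or placebo (94mg per pill) three times a day with each meal", and the arm table has once-daily dosing for the healthy elderly and MCI methylene blue (MB) arms.

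**Supply before visit 2.** "Subject will be given labeled pill organizers with pills to take on days 1 through 14".

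**Relation to the earlier trial.** Item 3 reports favourable cognitive and memory findings from the sponsor's 280 mg trial in young volunteers. It names as a difference the present trial's "daily MB dose for 2 to 12 weeks (as opposed to healthy subjects and single dose".

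**The concern.** With immediate-release capsules in divided doses, the drug level can move within the day. The plan allows one subject to be scanned soon after a capsule and another before the first capsule of the morning. It also allows one subject's week-2 and week-12 sessions to fall at different points of the dosing day.

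The protocol's own background makes a short-term effect plausible, because the sponsor reports favourable findings in a trial that it describes as single dose, with the same kinds of imaging readout. Three things are therefore at stake:

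- **Precision.** If the readouts respond to the current level, varying intervals add variance in the MB arm that placebo does not share.
- **Comparability.** A difference between week 2 and week 12 could partly reflect when in the dosing day each session was held.
- **Attribution.** Item 3 presents repeated daily dosing as what is new. A positive result could not be assigned to effects built up over two weeks rather than to the most recent capsule. If the interval is not recorded, it cannot reliably be recovered afterwards.

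**Working it through.** The documents give no half-life, sample size, SD or effect size, so there is no figure of the plan to reproduce. What follows is illustrative.

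**Inputs from the documents.** Three 94 mg capsules a day with meals: 3 × 94 = 282 mg, which agrees with the stated daily amount. Capsule supply covers days 1 to 14. Visit 2 is at two weeks ± 3 days, so about days 11 to 17.

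**Assumptions.** Meals at 08:00, 13:00 and 18:00; instant absorption; first-order decay with half-life t; steady state. Levels are in units of one capsule.

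**1. Trough against one hour after the morning capsule.** Just before 08:00 the last three capsules are 14, 19 and 24 h old, so

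T = (2^(−14/t) + 2^(−19/t) + 2^(−24/t)) / (1 − 2^(−24/t)).

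At 09:00, with the morning capsule taken, A = (T + 1) × 2^(−1/t).

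| t (h) | T | A | A/T |
|---|---|---|---|
| 3 | 0.056 | 0.838 | 15 |
| 6 | 0.397 | 1.245 | 3.1 |
| 12 | 1.372 | 2.239 | 1.6 |
| 24 | 3.490 | 4.362 | 1.25 |

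Example, t = 6: T = (0.1984 + 0.1114 + 0.0625)/0.9375 = 0.397; A = 1.397 × 0.891 = 1.245; ratio 3.1.

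**2. Share of the 09:00 level from that morning's capsule,** 2^(−1/t)/A: 95%, 72%, 42% and 22% for t = 3, 6, 12 and 24 h.

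**3. Spread between 09:00 and 17:00 with capsules taken as scheduled.** The low point is just before 13:00, B = (T + 1) × 2^(−5/t), and the high point just after, B + 1. The ratio (B + 1)/B is 1.333/0.333 = 4.0, 1.784/0.784 = 2.3, 2.777/1.777 = 1.6 and 4.886/3.886 = 1.26 for the same half-lives.

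**4. If dosing were once daily,** as two rows of the arm table say, the level 24 h after a capsule relative to 1 h after it is 2^(−23/t): 0.005, 0.07, 0.265 and 0.51. The spread widens.

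**5. End of supply.** If the last capsule is at 18:00 on day 14, a 09:00 scan on day 15 is 6 + 9 = 15 h later, and a 17:00 scan on day 17 is 6 + 24 + 24 + 17 = 71 h later. Relative to the level just after that last capsule, 2^(−15/t) = 0.03, 0.18, 0.42 and 0.65, while 2^(−71/t) is below 0.001 for 3 and 6 h, 0.02 for 12 h and 0.13 for 24 h. Late visits inside the window could therefore matter more than timing within the day.

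**6. Frequency wording.** Read literally, three 94 mg pills three times a day is 9 × 94 = 846 mg, against 282 mg elsewhere. The passages contradict each other.

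**The case against.** The strongest reply is that the trial is randomised and double-blind, so session timing should be balanced between arms on average. Items 2 and 4 ask whether daily dosing improves the outcomes; they do not ask for an effect net of the latest capsule. This stands. A reader might infer that the week-2 result is invalid, or cannot be read as the effect of two weeks of treatment. The documents do not support that: the contrast validly estimates the effect of being on the regimen.

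A reader might also infer that peak and trough sessions are in fact mixed. The text permits mixing but does not show it; sessions may in practice be held at a consistent hour.

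The size is easily overstated too. Decay from 1 h to 14 h after a single capsule with none between, 2^(−13/t), gives 0.22, 0.47 and 0.69 for 6, 12 and 24 h, or about 4.5-, 2.1- and 1.5-fold. That is a hypothetical worst case, because it sets the morning trough against an evening capsule, when a scan is unlikely. A subject who breakfasts as usual has also taken a capsule. And all these ratios are drug levels; nothing in the documents links level to fMRI or test response.

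Finally, the earlier trial gave 280 mg at once and one capsule here is 94 mg, so an acute effect is plausible rather than established.

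None of this supplies the missing interval, the missing record or the missing analysis term.

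**Conclusion.** The gap is real and of moderate weight. The plan neither standardises nor records the interval from last capsule to the visit 2 and 3 assessments. The consequences are possible extra variance in the MB arm, weaker comparability of weeks 2 and 12, and no means of attributing a positive result to cumulative rather than recent-capsule action. Validity of the randomised contrast is not in question.

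The size cannot be fixed from the documents. Under the assumed meal times and decay model, the trough-to-morning contrast in level is about 3.1-, 1.6- and 1.25-fold for half-lives of 6, 12 and 24 h: large if the half-life is short, modest if it is long. The effect on the outcomes is unquantified. The inconsistent dosing frequency does not remove the point, since once-daily dosing would allow longer intervals. The 14-day supply compounds it, because the visit window extends past it.

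**What to change.** - **Item 6 (Step by Step) and the outcome time frames:** hold each subject's visits at about the same time of day. For visits 2 and 3, start assessments within one interval after a scheduled capsule, chosen by the sponsor and the same in both arms.
- **Data collection:** record the clock time of the last capsule and of each scan and test.
- **Data Analysis Plan:** add a sensitivity analysis that uses the recorded interval.
- **Item 4:** describe the result as an on-regimen effect at that interval, not as a purely cumulative effect. A fixed interval standardises the measurement but does not by itself separate acute from cumulative action.
- **Reconcile:** the dosing-frequency wording in Step by Step and Intervention Groups, and the days 1 to 14 supply with the three days that the visit 2 window adds. The sponsor must decide which wording stands.

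The cost is less flexible scanner booking and a few recorded times per visit.

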
scanner:

Delayed match-to-sample memory task: The DMS task measures reaction time in terms of memory retrieval latency. The subject views a 6x6 pattern for 4 seconds. After six seconds, the subject is presented with two patterns and the subject presses the left or right button based on whether the picture on the left or the right is the same as the previous picture. The correct and incorrect answers are recorded. This exercise is repeated with 22 random patterns for approximately 10 mins.

Face-Name Task: The subject is shown blocks of stimuli where a novel or familiar face is paired with a name. In a later run, the subjects are asked whether the correct name is matched with the correct face. The correct and incorrect answers are recorded. The acquisition of data is divided into encoding and recognition tasks. This exercise is repeated many times lasting about 10 minutes.

Psychomotor vigilance task: The PVT measures attention and time-on-task effects. The subject receives a visual cue that alerts them to press a button as fast as possible. The reaction time is recorded. A rest period follows for 4-8 seconds. This exercise is repeated 30 times, lasting about 7-10 minutes.

Subject behavioral data (ie. Correct responses, reaction time) will be recorded simultaneously while the MRI data is acquired by a computer.

For CBF, the subject is instructed to close his or her eyes and relax in the scanner without falling asleep for 5-10 minutes.

For resting-state fMRI, the subject is told to close eyes and not to think about a particular topic, lasting about 10 minutes.

In addition, CBF will be measured during inhalation of medical-grade 5% CO2 in air for 3-5 minutes for calibration on all three visits. Standard anatomical MRI will also be acquired for co-registration. Diffusion tensor imaging (DTI) (5-7minutes) will also be acquired at one of the three visits.

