**Tertiary Outcome Measures:**

Functional Connectivity (resting state) fMRI measures

[Time Frame: baseline, 2 weeks ± 3 days, 12 weeks ± 15 days]

fMRI measurements will be obtained while the subject rests in the scanner

CO2 challenge: Cerebral blood flow measurements will be acquired during a brief (3-5 minutes) inhalation of medical-grade 5% CO2 in air for fMRI signal calibration purposes.

[Time Frame: baseline, 2 weeks ± 3 days, 12 weeks ± 15 days ]

Data Analysis Plan: Statistical parametric analysis will be performed to generate activation maps using established fMRI software. Task-evoked changes in brain activities will be analyzed and contrasted between placebo and MB conditions. ANOVAs, paired t and 2-sample t-tests will be used in analyzing the reaction times and success/failure rates in the DMS, FNT and PVT, with blocks (pre-MB vs. post-MB) as a within-subject variable and treatment (MB vs. Placebo) as a between-subject variable. Paired t-test will be used for group comparison with  $p < 0.05$  (False Discovery Rate  $q < 0.05$ ) considered statistically significant.

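### Face-Name pairs and story tests are repeated with no stated new material, and the planned paired t-test would credit any re-exposure gain to methylene blue

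*Combined protocol and SAP*

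**What the plan says.** Under Primary Outcome Measures, the episodic-memory entry reads "Face-Name Task behavioral (ie. correct recalls) and fMRI measures will be acquired simultaneously", and the TARCC battery is listed there too. Both are timed at baseline, week 2 and week 12. Item 4 instead calls the neuropsychological tests secondary, but the Face-Name task is primary in both places.

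Item 6 (Step by Step) gives "logical memory I, logical memory II, verbal fluency/COWA" among the examples in the baseline battery. At week 2, "another neuropsychological tests and MRI scan will be obtained". At the optional visit 3, "the subject will complete the subset of neuropsychological tests completed in visit 1" and some of the visit 1 scans. No test form is named for any visit.

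The Face-Name description says "The subject is shown blocks of stimuli where a novel or familiar face is paired with a name", followed by a later recognition run. It does not say whether the set changes between visits. The delayed match-to-sample task is described differently: "This exercise is repeated with 22 random patterns".

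The Data Analysis Plan specifies ANOVAs, paired and two-sample t-tests, "with blocks (pre-MB vs. post-MB) as a within-subject variable", and treatment as a between-subject factor. Its closing sentence names a paired t-test for comparing groups at the 0.05 level with false discovery rate control.

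**The concern.** A recall or recognition score taken a second time can rise for reasons unrelated to drug. The subject knows the procedure and, if the material returns, knows some of the answers. For the Face-Name task this would also affect imaging: a face shown as novel at visit 1 is no longer novel if it reappears at visit 2, the first scan on treatment.

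Two things are at stake. First, a pre/post test within the MB arm cannot separate the retest gain from a drug effect, and the plan's wording permits that test to carry the conclusion. Second, items already known from baseline have little room to show better learning on drug, which could hide a real difference between arms.

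The healthy elderly, MCI and AD groups come from TARCC, of whose participants Item 3 says "These subjects all have longitudinal psychometrics". They may already know the battery. Item 6 names no TARCC source for the healthy middle-aged group, so practice gains may differ between populations.

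**Working it through.** The documents give no sample size, effect size, SD, item count or retest correlation, so there is no plan figure to reproduce. **Every number below is an illustration on assumed inputs**, with two-sided alpha 0.05 and, for simulated rates, 20,000 trials per setting.

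**1. What cancels and what does not.** Let g be the average retest gain, equal in both arms, and δ the MB effect.
- Change on MB = g + δ; change on placebo = g.
- Between-arm difference in change = (g + δ) − g = δ.
- Within-arm pre/post change on MB = g + δ, which equals g when MB does nothing.

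**2. Additive gain.** Assume score SD 1 and retest correlation 0.7, so the SD of change is √(2 × (1 − 0.7)) = 0.775. The within-arm t-test has noncentrality g√n / 0.775; for g = 0.2 and n = 10 this is 0.2 × 3.162 / 0.775 = 0.82. Simulated rejection rates with no MB effect:

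| n per arm | g (SD) | Within MB arm, pre/post | Between arms, change |
|---|---|---|---|
| 10 | 0.2 | 12% | 5.2% |
| 10 | 0.4 | 31% | 5.0% |
| 20 | 0.2 | 20% | 4.9% |
| 20 | 0.4 | 60% | 4.8% |
| 30 | 0.2 | 28% | 4.7% |
| 30 | 0.4 | 79% | 4.8% |

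**3. Reused items.** Suppose a share c of items is remembered from visit 1 and answered correctly whatever the treatment. The post-treatment success probability is then c + (1 − c)(p + d), where p is the subject's accuracy and d the MB gain. Assume 30 items, mean p of 0.6 to 0.8, between-subject SD 0.10, d = 0.05 and 15 per arm.
- With d = 0, the pre/post gain is c(1 − p). At p = 0.7 and c = 0.2 it is 0.2 × 0.3 = 0.06. The simulated SD of change is about 0.114, so the noncentrality is 0.06 × √15 / 0.114 = 2.04, and the test rejects in 48% of trials.
- Over p = 0.6 to 0.8, within-arm false-positive rates are about 11–21%, 31–65% and 60–94% at c = 0.1, 0.2 and 0.3. The between-arm test stays at about 5%.
- With d = 0.05, the between-arm difference is (1 − c)d: 0.045, 0.040 and 0.035. At a fixed SD the sample size needed rises by 1/(1 − c)² = 1.23, 1.56 and 2.04 times. In simulation the ratios are about 1.2, 1.5 and 1.9–2.0, because the SD of change falls slightly.

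**4. Ceiling.** If scores are capped 1 SD above the baseline mean, a true 0.5 SD effect appears as 0.39, 0.32 and 0.24 SD at practice gains of 0, 0.4 and 0.8 SD. The first figure is the loss from the cap alone; the further fall is due to practice.

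**The case against.** A reader might infer that the same faces and stories are reused. The documents do not say so. The visit 3 sentence covers an optional visit, names tests rather than items and leaves the subset undefined; story recall may not be in it. Because the Face-Name task is defined by novelty, new faces may well have been intended. The random patterns in the match-to-sample task may describe trials within a session, so that contrast proves little. This objection stands: the gap is silence, not a stated choice.

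A reader might also infer that the MB-placebo comparison is biased, or diluted by a known amount. Neither is supported. Each population has a randomised placebo arm, and a common additive gain cancels. Dilution needs a ceiling or remembered items that do not respond to drug, and no document figure fixes the share. The baseline battery may be given up to two months before the scan, so the stories could be roughly ten weeks old at week 2. Carry-over may also be weaker in impaired subjects. Moreover, on the step 3 assumptions at p = 0.7, between-arm power is only about 21% with no carry-over and about 13% at c = 0.3, so most of the risk of missing an effect lies elsewhere.

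Finally, the paired-test wording may be loose drafting, since the same paragraph names two-sample tests and a treatment factor, and it would need correcting even with new stimuli. Both points are fair. But the plan does not say which test decides, and the one it attaches to the significance threshold is the paired test. Repeating a primary memory task after about two weeks gives that choice practical consequences.

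**Conclusion.** The point holds as an omission joined to an ambiguous decision rule. The plan repeats a primary episodic-memory task and a battery whose examples include story recall, requires neither new face-name pairs nor alternate forms, and names a paired t-test for the group comparison. If that test is applied pre versus post within an arm, any retest gain is counted as benefit. Under the assumptions shown, false-positive rates run from about 11% with modest carry-over to above 90% with heavy carry-over and lower baseline accuracy. The between-arm comparison of change stays near 5% throughout.

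Loss of the MB-placebo difference is possible if items are reused. Its size cannot be estimated from the documents; the 10% to 30% figures only restate the assumed carry-over share.

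**What to change.** **Data Analysis Plan.** State that every conclusion about MB rests on the between-arm difference in change, tested by the treatment-by-time interaction or a baseline-adjusted two-sample comparison. Label within-arm pre/post tests as descriptive. This costs only wording and is the more important change, because it also covers general practice effects that new stimuli would not remove.

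**Face-Name Task.** Use a different set, matched for difficulty, at each visit. Counterbalance set order, balance it between arms within each population, and include set as a model term. If new sets were already intended, one sentence saying so settles that part.

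**Battery.** Name the tests and forms used at each visit, with alternate story forms where an equivalent exists. Where none exists, keep the test and interpret only the MB-placebo difference.

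The cost is preparing two further face-name sets, with no extra scans, visits or subjects. Sets that differ in difficulty add variance: counterbalancing removes the bias but not that noise, which is why set belongs in the model. For example, if set difficulty had an SD of 0.03 to 0.05 (assumed) and set were ignored, two sets would add 2 × 0.03² = 0.0018 to 2 × 0.05² = 0.0050 to a change-score variance of about 0.0134 (step 3 at p = 0.7, c = 0), or roughly 13% to 37%.
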